8. STATISTICAL METHODOLOGY

8.1. General

Listings will be provided for all data captured in the database, with the exception of medical history. Listings will include all subjects assigned to the all subjects population and include data up to the point of study completion or discontinuation. Subjects are generally considered to have completed the study if they complete the scheduled follow-up visit (rather than early termination visit). Any subject who discontinues the study will be identified accordingly in the listings. Summaries and statistical analyses will include the subjects assigned to the relevant population based on data type.

Data analysis will be performed using the SAS® statistical software package Version 9.4 (or higher if a new version is issued during the study).

Analysis Data Model (ADaM) datasets will be prepared using Clinical Data Interchange Standards Consortium (CDISC) ADaM Version 2.1 (or higher if a new version is issued during the study) and CDISC ADaM Implementation Guide Version 1.1 (or higher if a new version is issued during the study). Pinnacle 21 Community Validator Version 3.1.2 (or higher if a new version is issued during the study) will be utilised to ensure compliance with CDISC standards.

For all statistical analyses, the hypothesis testing will be 2-sided and carried out on 0.05 significance level, unless specifically stated otherwise.

Caution should be used when interpreting results from the statistical analyses conducted in this study because the sample size is not based on power calculations.

Where reference is made to 'valid' data, this refers to non-missing data which meet the predetermined criteria (eg, are not flagged for exclusion).

Where reference is made to 'all calculations', this includes, but is not limited to, summary statistics, statistical analyses, baseline derivation, changes from baseline, and any parameter derivations.

All figures will be produced on linear-linear or discrete-linear scales, as applicable, unless specifically stated otherwise.

Any clock changes will be accounted for in the derivation of actual time postdose, adverse event (AE) duration, and AE onset time.

8.1.1. Handling of Data Quality Issues Due to Coronavirus Disease 2019 and Related Restrictions

Due to COVID-19 and related restrictions, there is a high risk for impact to data integrity, with the recognised potential for:

- Missed visits, caused by, for example,:

- Subject unable to travel to site due to restrictions, the need to quarantine, or COVID-19 infection
- Subject unwilling to go to site due to fear of COVID-19 infection
- Site postponing subject's visit due to investigator not being available (eg, if they have been dispatched to hospital handling COVID-19 infections)
- Site unable to replenish supply of investigational product
- Incomplete data entry by sites due to limited resources to support study or no access to source documents or to eCRF
- Outstanding source document verification (SDV) due to sponsor or country restrictions on remote SDV, or no or limited access to site(s) for on-site visits
- Unanswered queries

At the time of the reporting of the study results, all protocol deviations due to COVID-19 or related restriction will be assessed for their severity and impact on the analyses. If needed, appropriate statistical methods will be applied as a mitigating action (eg, data might be categorised into 2 analysis groups, with and without COVID-19 and related restrictions impact); however, this will exclude any imputations of the missing values. Any mitigating actions will be agreed with Kyorin Pharmaceutical Company Limited in advance and identified in the CSR.

8.1.2. Calculation of the Summary Statistics

For continuous data the following rules will be applied:

- Missing values will not be imputed, unless specifically stated otherwise.
- Unrounded data will be used in the calculation of summary statistics.
- If the number of subjects with valid observations ($n < 3$), summary statistics will not be calculated, with the exception of n , minimum, and maximum.
- In general, as early termination data are not associated with any scheduled timepoint, they will be excluded from all calculations of summary statistics. Exceptions may be made where justified.

For categorical data the following rules will be applied:

- For ordered categorical data (eg, AE severity), all categories between the possible minimum and maximum categories will be included, even if $n = 0$ for a given category.
- For non-ordered categorical data (eg, race), only those categories for which there is at least 1 subject represented will be included; unless specifically stated otherwise.

- Missing values will not be imputed, unless specifically stated otherwise. A ‘missing’ category will be included for any parameter for which information is missing. This will ensure that the population size totals are consistent across different parameters.

8.1.3. Triplicate Readings

For vital signs data only, where triplicate readings are taken, the median of triplicate readings will replace the separate individual triplicate readings in all calculations.

For 12-lead ECG data only, where triplicate readings are taken, the mean of triplicate readings will replace the separate individual triplicate readings in all calculations.

In case of incomplete triplicate readings (eg, only 2 out of 3 readings were recorded), the mean and/or median will be calculated, as appropriate, based on the number of readings available.

8.1.4. Repeat and Unscheduled Readings

For vital signs and 12-lead ECG data only, any predose value recorded in addition to the original value or a postdose value recorded within 15 minutes of the original value will be defined as a repeat value; any postdose value recorded more than 15 minutes after the original value will be defined as an unscheduled value. For all other data types (eg, laboratory parameters), any value recorded in addition to the original value will be defined as an unscheduled value.

The original value will be replaced by the last associated repeat value in all calculations, with the exception of the 12-lead ECG outlier analysis (see [Section 8.7.4](#)).

As unscheduled values are not associated with any scheduled timepoint, they will be excluded from all calculations, with the exception of the baseline derivation (see [Section 8.1.5](#)) and 12-lead ECG outlier analysis (see [Section 8.7.4](#)).

8.1.5. Definitions of Baseline and Change from Baseline

The baseline will be defined as the last value recorded prior to the first dose. If the date/time of the value is incomplete or missing, it will be excluded from the baseline calculation, unless the incomplete date/time indicates the value was recorded prior to the first dose.

Individual changes from baseline will be calculated by subtracting the individual subject’s baseline value from the value at the postdose timepoint.

The summary statistics for change from baseline will be derived from individual subjects’ values (eg, mean change from baseline will be the mean of the individual changes from baseline for all subjects, rather than difference between the mean value at the postdose timepoint and mean value at baseline).

See [Section 8.1.4](#) for more detail on handling repeat and unscheduled readings in the calculations. See [Section 8.1.3](#) for more detail on handling of triplicate readings in the calculations.

8.2. Subject Disposition and Population Assignment

Subject disposition and population assignment will be listed.

A summary table by treatment for Parts A and B and by overall for Part C will be provided, based on the safety population.

Screen failure data summary table will be provided separately, based on the all subjects population.

8.3. Screening Demographics

The screening demographics including age, sex, race, ethnicity, height, body weight, and body mass index will be listed.

A summary table by treatment for Parts A and B and by overall for Part C will be provided, based on the safety population.

8.4. Prior and Concomitant Medication

Prior medication will be defined as medication that ends prior to the first dose. Concomitant medication will be defined as medication that starts during or after the first dose or starts but does not end prior to the first dose.

Prior and concomitant medications will be coded using the World Health Organization Drug Dictionary (WHODrug) Global, Format B3, Version March 2021 (or later if a new version is issued during the study; see the data management plan [DMP] for more details). Prior and concomitant medications will be listed.

8.5. Pharmacokinetic Assessments

8.5.1. Pharmacokinetic Analysis

The following PK parameters will be determined where possible from the plasma concentrations of **CCI** itraconazole and hydroxy-itraconazole using noncompartmental methods in validated software program Phoenix WinNonlin (Certara, Version 8.1 or higher):

Part A (Day 1), Part B (Day 1) and Part C (Days 1 and 11) (CCI)

Parameter	Units ^a	Definition
AUC _{0-t_{last}}	ng*h/mL	area under the concentration-time curve from time 0 to the time of the last quantifiable concentration (t _{last}) ^b
DAUC _{0-t_{last}}	ng*h/mL/mg	area under the concentration-time curve from time 0 to the time of the last quantifiable concentration (t _{last}) normalized by dose administered ^e
AUC _{0-τ}	ng*h/mL	area under the concentration-time curve over a dosing interval (τ) ^d
AUC _{0-∞}	ng*h/mL	area under the concentration-time curve from time 0 extrapolated to infinity ^c
DAUC _{0-∞}	ng*h/mL/mg	area under the concentration-time curve from time 0 extrapolated to infinity normalized by dose administered ^{ce}
%AUC _{extrap}	%	percentage of area under the concentration-time curve due to extrapolation from the last quantifiable concentration to infinity
C _{max}	ng/mL	maximum observed concentration
DC _{max}	ng/mL/mg	maximum observed concentration normalized by dose administered ^e
t _{max}	h	time of the maximum observed concentration
t _{1/2}	h	apparent terminal elimination half-life
CL/F	L/h	apparent total clearance
V _z /F	L	apparent volume of distribution during the terminal phase

^a Units are based on concentration units (provided by the bioanalytical lab or preferred units for presentation of PK parameters) and dose units used in the study.

^b The AUC will be calculated using the linear trapezoidal rule for increasing concentrations and the logarithmic rule for decreasing concentrations (linear up/log down rule).

^c Based on the last observed quantifiable concentration

^d Part B Day 1 only – not required for Parts A and C

^e Not required for Part C

Part B (Day 14) (CCI)

Parameter	Units ^a	Definition
AUC _{0-t_{last}}	ng*h/mL	area under the concentration-time curve from time 0 to the time of the last quantifiable concentration (t_{last}) ^b
DAUC _{0-t_{last}}	ng*h/mL/mg	area under the concentration-time curve from time 0 to the time of the last quantifiable concentration (t_{last}) normalized by dose administered
AUC _{0-τ}	ng*h/mL	area under the concentration-time curve over a dosing interval (τ)
DAUC _{0-τ}	ng*h/mL/mg	area under the concentration-time curve over a dosing interval (τ) normalized by dose administered
C _{max}	ng/mL	maximum observed concentration
DC _{max}	ng/mL	maximum observed concentration normalized by dose administered
C _{min}	ng/mL	minimum observed concentration during a dosing interval
t _{max}	h	time of the maximum observed concentration
t _{1/2}	h	apparent terminal elimination half-life
CL/F	L/h	apparent total clearance
V _z /F	L	apparent volume of distribution during the terminal phase
AR _{AUC_{0-τ}}		observed accumulation ratio based on AUC _{0-τ}
AR _{C_{max}}		observed accumulation ratio based on C _{max} during the dosing interval

The dosing interval τ is 24 hours.

^a Units are based on concentration units (provided by the bioanalytical lab or preferred units for presentation of PK parameters) and dose units used in the study.

^b Area under the concentration-time curve will be calculated using the linear trapezoidal rule for increasing concentrations and the logarithmic rule for decreasing concentrations (linear up/log down rule).

Part C Day 11 (Itraconazole and Hydroxy-Itraconazole)

Parameter	Units ^a	Definition
AUC _{0-τ}	ng*h/mL	area under the concentration-time curve over a dosing interval (τ) ^b
C _{max}	ng/mL	maximum observed concentration
t _{max}	h	time of the maximum observed concentration

^a Units are based on concentration units (provided by the bioanalytical lab or preferred units for presentation of PK parameters) and dose units used in the study.

^b The AUC will be calculated using the linear trapezoidal rule for increasing concentrations and the logarithmic rule for decreasing concentrations (linear up/log down rule).

Additional PK parameters may be determined where appropriate.

The PK analysis will be carried out where possible using the actual dose of KRP-A218 administered (mg) and actual postdose blood sampling times. If an actual time is missing, the sample concentration result will be treated as missing unless there is scientific justification to include the result using the nominal time.

The parameters C_{max}, C_{min}, and t_{max} will be obtained directly from the concentration-time profiles. If C_{max} occurs at more than 1 timepoint, t_{max} will be assigned to the first occurrence of C_{max}.

The accumulation ratios (AR_{AUC0- τ} and AR_{C_{max}}) will be calculated as follows:

$$AR_{AUC0-\tau} = AUC_{0-\tau} \text{ Day 14} / AUC_{0-\tau} \text{ Day 1}$$

$$AR_{C_{max}} = C_{max} \text{ Day 14} / C_{max} \text{ Day 1}$$

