1.3. Summary of Clinical Experience

In this ongoing Phase 1 study, as of 27 August 2021, a total of 27 subjects have been dosed and have completed the study. Seven subjects have received 1 mg KRP-A218 or placebo under fasted conditions (Group A1), 8 male subjects have received 3 mg KRP-A218 or placebo under fasted and fed conditions (Group A2a), 4 female subjects have received 3 mg KRP-A218 or placebo under fasted conditions (Group A2b), and 8 subjects have received 6 mg KRP-A218 or placebo under fasted conditions (Group A3). For dose escalation decision, a minimum of 6 subject's data per group has been evaluated, including 7 subjects in Group A1 (1 mg), 6 subjects in Group A2a (3 mg), and 8 subjects in Group A3 (6 mg). There were no serious adverse events (SAEs), deaths, or no other significant adverse events (AEs). The AEs experienced by these subjects have included headache, loose stools, cold symptoms, aching lower legs, abdominal pain, stomach ache, drowsiness, blood visible when passing stool sample, and sore throat. All were transient and either mild or moderate in severity.

Preliminary PK parameters determined from the ongoing Phase 1 study are presented in [Table 3](#).

Table 3: Geometric Mean (CV%) PK Parameters of CCI Following Single Oral Dose Administration of KRP-A218 to Healthy Subjects*

Parameter (units)	1 mg [Fasted]	3 mg [Fasted]	3 mg [Fed]	6 mg [Fasted]
AUC _{0-tlast} (ng·h/mL)	198 (18.5)	540 (27.0)	570 (25.6)	1160 (28.4)
AUC _{0-∞} (ng·h/mL)	210 (18.6)	564 (30.1)	596 (28.0)	1230 (28.4)
AUC _{0-24h} (ng·h/mL)	145 (19.5)	388 (21.4)	393 (19.1)	813 (27.9)
C _{max} (ng/mL)	11.9 (30.3)	29.8 (23.5)	29.5 (15.2)	60.3 (26.5)
t _{max} ** (h)	3.00 (2.00-4.00)	3.50 (2.00-4.00)	3.50 (3.00-8.00)	3.50 (1.50-4.00)
t _{1/2} (h)	18.2 (11.5)	15.2 (20.3)	14.8 (18.4)	16.9 (9.68)

Abbreviations: AUC_{0-∞} = area under the concentration-time curve from time 0 extrapolated to infinity; AUC_{0-24h} = area under the concentration-time curve from time 0 to 24 hours; AUC_{0-tlast} = area under the concentration-time curve from time 0 to the time of the last quantifiable concentration; C_{max} = maximum observed concentration; CV% = coefficient of variation; PK = pharmacokinetic; t_{1/2} = apparent terminal elimination half-life; t_{max} = time of the maximum observed concentration.

* As per protocol, a minimum of 6 subjects (4 active subjects) data per group was evaluated for dose escalation decision.

** Median (min-max)

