3.1.2. Part B (Multiple Ascending Dose Study)

Part B will comprise a double-blind, randomised, placebo-controlled, multiple-dose, sequential-group, escalating-dose design, enrolling healthy male subjects. Overall, 40 subjects will be studied in 4 groups (Groups B1 to B4), with each group consisting of 10 male subjects. Part B may start after completion of Group A3, at dose equal to or less than given in Groups A1 to A3.

Potential subjects will be screened to assess their eligibility to enter the study within 28 days prior to the first dose administration. Each subject will participate in 1 treatment period only and reside at the CRU from Day -1 (the day before dosing) until the morning of Day 17 (following assessments at 72 hours after final dosing).

All subjects will return for a follow-up visit 7 to 10 days after their final dose. The follow-up period may be extended depending on the observed $t_{1/2}$ of CCI [REDACTED]

In each of Groups B1 to B4, 8 subjects will receive KRP-A218 and 2 subjects will receive placebo in accordance with a randomisation schedule. The dietary state for dosing in Part B will be subject to review of the PK data from the fed/fasted comparison in Part A. For all subjects, dosing will occur on Days 1 to 14. The planned dosing frequency is once per day, however the dosing frequency in Part B may be changed following review of data from groups in Part A ([Section 3.4](#)). On Day 14, the last dose will be the morning dose regardless of the dosing frequency (QD, BID, TID).

[figure not shown]
The total daily dose administered will not exceed an exposure shown to be safe and well tolerated in Part A.

Based on the ongoing review of the safety, tolerability, and PK results, additional nonresidential visits may be required. The number of additional visits per subject will not exceed 3 and will not extend beyond 28 days after each final dosing occasion. All subjects may stay in the CRU even outside treatment period due to COVID-19 risks.

All groups in Part B will receive the IMP using a sentinel approach, as described in [Section 5.3](#). Details regarding dose escalation are presented in [Section 3.5](#).

An overview of the study design is shown in [Figure 3](#), and the planned dose levels in [Figure 5](#).

A Schedule of Assessments is presented in [Appendix 6](#).

Figure 3: Study Schematic (Part B)

The follow-up period may be extended depending on the observed $t_{1/2}$ of CCI.

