Appendix 3: Total Blood Volume

The following blood volumes will be withdrawn from each subject in Part A.

	Volume per blood sample (mL)	Maximum number of blood samples			Total amount of blood (mL)		
		A1, A2b (f), A3, A4	A5	A2a (m)	A1, A2b (f), A3, A4	A5	A2a (m)
Haematology, Clinical chemistry, and Coagulation ^{a, b}	9.3	5	5	8	46.5	46.5	74.4
Serology	3.5	1	1	1	3.5	3.5	3.5
CCl pharmacokinetics	2	16	16	32	32	32	64
Metabolite profiling	2	-	7	7	-	14	14
Pharmacogenetics	10	1	1	1	10	10	10
Total:					92	106	165.9

Abbreviations: f = females; m = males.

^a Includes blood collected for follicle-stimulating hormone and serum pregnancy testing at screening from subjects in Group A2b.

^b Includes a 1.8 mL sample for activated partial thromboplastin time, prothrombin time/international normalised ratio, and fibrinogen.

If extra blood samples are required, the maximum blood volume to be withdrawn per subject will not exceed 500 mL.

The following blood volumes will be withdrawn from each subject in Part B.

	Volume per blood sample (mL)	Maximum number of blood samples		Total amount of blood (mL)	
		B1	B2 to B4	B1	B2 to B4
Haematology, Clinical chemistry, and Coagulation ^a	9.3	9	9	83.7	83.7
Serology	3.5	1	1	3.5	3.5
CCI pharmacokinetics	2	40	40	80	80
Metabolite profiling	2	8	-	16	-
Pharmacogenetics	10	1	1	10	10
Total:				193.2	177.2

^a Includes a 1.8 mL sample for activated partial thromboplastin time, prothrombin time/international normalised ratio, and fibrinogen.

If extra blood samples are required, the maximum blood volume to be withdrawn per subject will not exceed 500 mL.

The following blood volumes will be withdrawn from each subject in Part C.

	Volume per blood sample (mL)	Maximum number of blood samples	Total amount of blood (mL)
		C1	C1
Haematology, Clinical chemistry, and Coagulation ^a	9.3	8	74.4
Serology	3.5	1	3.5
CC1 pharmacokinetics	2	32	64
Itraconazole and hydroxy-itraconazole pharmacokinetics	2	16	32
Metabolite profiling	2	14	28
Pharmacogenetics	10	1	10
Total:			211.9

^a Includes a 1.8 mL sample for activated partial thromboplastin time, prothrombin time/international normalised ratio, and fibrinogen.

If extra blood samples are required, the maximum blood volume to be withdrawn per subject will not exceed 500 mL.

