^a Interim medical history.^b Subjects will receive the IMP once daily at the same time as Day 1 in the fasted state (at least 10 hours).^c Subjects will be fasted until 4 hours after dosing, after which time a meal will be provided.^d Collected in Group B1 only.^e Spot urine sample will be collected any time prior to dosing. 24-hour urine samples will be collected on 0 to 24 hours postdose on Day 14.^f Subjects will be fasted at least 6 hours before collection.

^g Faecal occult blood test will be performed once each during the following sampling periods: Screening, Day -1 to prior to dosing, 0 to 24, 24 to 96, 96 to 168, 168 to 240 hours postdose on Day 1, 240 hours postdose on Day 1 to 0 hours on Day 14, and 0 to 72 hours postdose on Day 14. On screening, faecal samples will be collected to confirm eligibility for enrollment. For the other sampling periods, faecal samples will be collected as far as possible.

^h To be assessed when collecting faecal samples for faecal occult blood test in the treatment period.

ⁱ Subjects should be supine for at least 5 minutes before blood pressure and pulse rate measurements.

^j To be measured in triplicate at approximately 2-minute intervals.

^k To be recorded after the subject has been supine and at rest for at least 5 minutes.

^l Full physical examination.

^m Symptom-directed physical examination.

ⁿ Immediately before dosing.

^o From waking-up to before dosing.

^p To be performed at approximately the same time as on Day 1.

^q From waking-up to before breakfast.

^r If the latest result during the treatment period is positive, faecal samples will be collected for faecal occult blood test at the follow-up visit (within -2 day), as far as possible.

^s Prior to discharge.

^t The follow-up period may be extended depending on the observed $t_{1/2}$ of **CCI**

Table 12: Schedule of Assessments-Part C (DDI) [Screening to Day4]

Day	Screening	Treatment Period 1																
		-28 to -2	-1	1	2	3	4	6	8	12	24	36	48	72				
Time Postdose (h)		Pre	0	0.25	0.5	0.75	1	1.5	2	3	4	6	8	12	24	36	48	72
Informed consent	X																	
Inclusion/exclusion criteria	X	X																
Demographic data	X																	
Medical history	X	X ^a																
Urinary drug and cotinine screen	X	X																
Alcohol breath test	X	X																
Serology	X																	
Height	X																	
KRP-A218 and itraconazole administration^r																		
KRP-A218			X ^b															

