8.5.2. Presentation of Pharmacokinetic Data

All PK concentrations and parameters will be listed.

Summary tables, arithmetic mean (+ standard deviation [SD]) figures, overlaying individual figures, and individual figures by treatment and time postdose will be provided for plasma

PK concentrations. All figures will be produced on both linear-linear and linear-logarithmic scales. The +SD bars will only be displayed on the linear-linear scale.

Summary tables by treatment will be provided for all PK parameters, with the exception of diagnostic regression-related PK parameters.

A subject may be excluded from the PK summary statistics and statistical analysis if the subject has an AE of vomiting that occurs at or before 2 times the median t_{max} .

If the actual time of sample collection deviates from the nominal time by more than $\pm 10\%$, the plasma/serum/whole blood concentration will be flagged and excluded from the summary statistics. Individual concentrations deemed to be anomalous will be flagged in the listings and excluded from the summary statistics.

For plasma/serum/whole blood concentration data, the following rules will apply:

- Values that are BLQ will be set to 0 for the calculation of summary statistics.
- Arithmetic mean or median values that are BLQ will be presented as 0.

For PK parameters, the following rule will apply:

- Geometric mean and coefficient of variation (CV) will not be calculated for t_{max} .

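### Part B Day 1 AUC0-∞, t1/2, CL/F and Vz/F come from a 24-hour profile of a compound with a 15–18 h half-life, and only judgement keeps them out of the summary tables

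*SAP*

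**What the plan says.** **Regimen and sampling.** Protocol 3.1.2: "The planned dosing frequency is once per day". The footnotes to Protocol Appendix 6, Table 11 add "Subjects will receive the IMP once daily at the same time as Day 1" and, for the daily PK samples on Days 2–13, "Immediately before dosing". SAP 8.5.1: "The dosing interval τ is 24 hours".

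**Parameters.** Protocol 2.2.2 and SAP 3.2 list t1/2, CL/F and Vz/F for Part B on Days 1 and 14, and AUC0-∞ for Day 1 only. The SAP 8.5.1 table headed "Part A (Day 1), Part B (Day 1) and Part C (Days 1 and 11" includes all four, and none of its footnotes exempts Part B Day 1 from them.

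**Controls.**
- SAP 8.5.1 determines parameters where possible.
- SAP 8.5.1.1 calculates λz only when the estimate is reliable, from at least 3 points with adjusted R² of at least 0.7. The start of the terminal phase is chosen by eye. The fitting span should, where possible, be at least 2 half-lives; if it is shorter, the CSR discusses robustness.
- SAP 8.5.1.2 allows AUC0-∞ and parameters derived from it to be excluded when extrapolation exceeds 20%, at the discretion of the sponsor or pharmacokineticist.

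**Reporting.** SAP 8.5.2: "Summary tables by treatment will be provided for all PK parameters, with the exception of diagnostic regression-related PK parameters". Protocol 8.3 likewise has PK parameters listed and summarised by treatment group.

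**The concern.** λz has to describe the terminal phase. With a half-life of 15–18 h and a median tmax of 3.0–3.5 h, a 24 h profile holds little of that phase, and the slope it yields mixes in the faster earlier decline. Every parameter that needs λz inherits the error.

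The Part B tables would then show t1/2 and CL/F under the same names for Day 1 (at most 24 h of data) and Day 14 (sampling to 72 h). A reader could take the difference as a change in elimination over time. That reading would come easily, because Protocol 1.2 reports slight time-dependent inhibition of CYP3A4 and a potential to induce it.

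The problem was foreseeable. The SAP was written after protocol version 5.0, which already contains Table 3, yet Part B Day 1 has no rule of its own.

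**Working it through.** **1. Length of the profile.** Appendix 3 allows 40 Part B PK samples. Table 11 gives 12 on Day 1 (predose to 12 h), 12 predose on Days 2–13 and 16 from Day 14: 12 + 12 + 16 = 40. The last sample before dose 2 is therefore the one at 24 h.

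**2. The protocol's own figure.** Table 4 uses R = 1.6, from the 6 mg half-life. R = 1/(1 − exp(−ln2 × 24/16.9)) = 1.597, and 1080 × 1.6 = 1728, given as 1730. Both reproduce.

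**3. Share of AUC0-∞ not observed.** Inputs are the geometric means and median tmax of Protocol 1.3, Table 3. Share beyond 24 h = 1 − AUC0-24h/AUC0-∞; share beyond tlast = 1 − AUC0-tlast/AUC0-∞.

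| | 1 mg | 3 mg fasted | 3 mg fed | 6 mg |
|---|---|---|---|---|
| AUC0-24h / AUC0-∞ (ng·h/mL) | 145/210 | 388/564 | 393/596 | 813/1230 |
| Beyond 24 h | 31.0% | 31.2% | 34.1% | 33.9% |
| Beyond tlast (Part A) | 5.7% | 4.3% | 4.4% | 5.7% |

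**4. Two-point check of a fit that stops at 24 h.** Assumption: mono-exponential decline after 24 h at the reported t1/2, so C24 = (AUC0-∞ − AUC0-24h) × ln2/t1/2. Apparent λz = ln(Cmax/C24)/(24 − tmax). Apparent AUC0-∞ = AUC0-24h + C24/λz. Span of a 4–24 h window = 20/apparent t1/2.

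At 6 mg:
- C24 = 417 × 0.693/16.9 = 17.1 ng/mL
- λz = ln(60.3/17.1)/20.5 = 0.0615 per h, so t1/2 = 11.3 h
- AUC0-∞ = 813 + 17.1/0.0615 ≈ 1091, which is 11.3% below 1230
- CL/F is high by 1230/1091 − 1 = 12.7%

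| | 1 mg | 3 mg fasted | 3 mg fed | 6 mg |
|---|---|---|---|---|
| Reported t1/2 (h) | 18.2 | 15.2 | 14.8 | 16.9 |
| C24 (ng/mL) | 2.48 | 8.03 | 9.51 | 17.1 |
| Apparent t1/2 (h) | 9.3 | 10.8 | 12.5 | 11.3 |
| AUC0-∞ error | −15% | −9% | −5% | −11% |
| CL/F error | +18% | +10% | +5% | +13% |
| Vz/F error | −40% | −22% | −11% | −25% |
| Apparent %AUCextrap | 18.6% | 24.4% | 30.5% | 25.5% |
| Apparent span, 4–24 h | 2.2 | 1.8 | 1.6 | 1.8 |

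Vz/F error = (CL/F ratio) × (apparent t1/2 / reported t1/2) − 1.

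**5. Would the SAP's checks catch it?** The 4–24, 6–24 and 8–24 h windows hold 5, 4 and 3 points, so the 3-point minimum is met. In a simulation calibrated to the 6 mg means (assumed CVs: 27% exposure, 10% half-life, 8% residual), 99.9% of 24 h profiles met the R² limit, with a median t1/2 of 12.0 h against a true 16.9 h. In the 1 mg column of step 4, extrapolation is below 20% and the span is above 2, although the apparent t1/2 is about half the reported one. In the other three columns the 20% limit is exceeded and the span is below 2, which leads to discretion and discussion.

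**The case against.** **The SAP's limits act on each profile's own fit.** A reader might set the 31–34% of Table 3 against the 20% limit, or divide the 16–20 h windows by the Part A half-life (0.88–1.35), and infer that every Day 1 profile must fail both checks. The documents do not support that. SAP 8.5.1.1 defines the span ratio by t1/2, most naturally that of the same fit, and %AUCextrap comes from the Day 1 profile. On that basis the figures are about 1.6–2.2 and 19–31%. This objection stands, but it does not remove the concern: the checks weaken as the fitted slope becomes more biased.

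**Controls exist.** The reliability condition is mandatory in wording and covers t1/2. %AUCextrap is in the main parameter table, so it would already be summarised alongside AUC0-∞. A span below 2 must be discussed. It would therefore be wrong to say that the plan is uncontrolled or compels biased summaries. What stands against it is that the reliability test is a judgement, exclusion above 20% is optional, and t1/2 is not derived from AUC0-∞, so the 20% rule does not clearly reach it.

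**The consequences are limited.** Neither document plans a Day 1 versus Day 14 comparison of t1/2 or CL/F, and Part A supplies single-dose values from 72 h sampling. This also stands, and it limits the weight of the point.

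**Conclusion.** The concern holds in a limited form. The plan permits, but does not require, summaries of Part B Day 1 AUC0-∞, t1/2, CL/F and Vz/F from a window too short for a 15–18 h half-life, and its numerical checks can be passed by values that are wrong.

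The 24 h window, the 31–34% share and the content of the rules are firm. The direction of bias is supported in all four columns. Its size (t1/2 about 9–12.5 h, AUC0-∞ about 5–15% low, CL/F about 5–18% high) is illustrative. It rests on preliminary geometric means from as few as 4 active subjects per group, on mono-exponential decline after 24 h, and on a line drawn from Cmax; a later fitting window may give less bias. Part B doses are not given in the documents, and no share of subjects is claimed.

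A reader might infer that Part B's main PK conclusions are at risk. They are not: AUC0-τ, Cmax, the accumulation ratios and the Day 14 dose-proportionality analysis do not use the Day 1 λz. Only descriptive secondary values are affected. The change should be made because it is cheap and the problem is predictable.

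**What to change.** Add to SAP 8.5.1.1 and 8.5.1.2: *If the Part B Day 1 profile ends at or before 24 h, the λz-dependent parameters (AUC0-∞, DAUC0-∞, t1/2, CL/F, Vz/F) will be listed with %AUCextrap and span ratio, but excluded from summary statistics and not compared with Day 14.*

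Making the existing 20% and 2-half-life limits binding would not be enough, as the 1 mg column shows. Keep Day 1 AUC0-τ, Cmax and tmax in the summaries, and assess accumulation from the planned ratios.

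Protocol 8.3 says that PK parameters are summarised. Either record the rule in SAP Section 10, which now reports no significant changes, or align Protocol 2.2.2 and 8.3 and SAP 3.2.

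**Cost.** Wording only: no new data, no endpoint removed, all values still listed. Day 1 summaries of these parameters are lost, including for any profile that would have been adequate. The rule would not apply if the dosing interval were lengthened, which Protocol 3.4 allows.
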